4.0 Study Aims

4.1 Primary Aim: Treatment Effectiveness. To evaluate the effectiveness of XR-NTX vs. O-NTX in producing a primary good clinical outcome, defined as abstinence or moderate drinking (≤ 2 drinks/day, men; ≤ 1 drink/day, women; and ≤ 2 heavy drinking occasions/month), during the final 20 of 24 weeks of primary care-based Medical Management for alcohol dependence.

Hypothesis: The rate of this good clinical outcome will be approximately twice as great among participants receiving XR-NTX compared with those receiving O-NTX.

4.2 Secondary Aim 1: Cost Effectiveness. To estimate the incremental cost effectiveness of XR-NTX vs. O-NTX both in conjunction with primary care-based Medical Management.

Hypothesis: XR-NTX treatment will be more cost effective than O-NTX.

Secondary Aim 2: Patient-Level Predictors of Effectiveness. To identify patient-level characteristics associated with effectiveness in both arms.

5.0 Study Design: A Randomized Comparative Effectiveness Trial to Evaluate XR-NTX vs. O-NTX for Alcohol Dependence in Primary Care

We propose a pragmatic randomized controlled trial to compare the effectiveness and incremental cost-effectiveness of XR-NTX vs. O-NTX as a component of primary care-based Medical Management of alcohol dependence among 234 adults. The 24 week treatment trial will assess monthly treatment retention, self-reported drinking outcomes, biomarkers, and costs. The primary effectiveness outcome is a moderate drinking good clinical outcome, defined as abstinence or moderate drinking (≤ 2 drinks/day, men; ≤ 1 drink/day, women, and ≤ 2 heavy drinking occasions/month), during weeks 5-24. A long-term follow-up assessment at week 48 will gather further drinking and cost data. The MM visit schedule and research assessment visits will occur as follows over 48 weeks (Table 2):

Table 2. Visit Frequency (weeks)	0	1 ⁺	3	5 ⁺	7	9 ⁺	13 ⁺	17 ⁺	21 ⁺	25	26	48
XR-NTX vs. O-NTX + MM visits	x [#]	x [#]	x	x	x	x	x	x	x	x	x [*]	
Research-only assessment visits							x [#]			x [#]		x [#]

- *Safety documentation research visit
- # Compensation provided
- + Medication Dispensed

6.0 Study Population

This study will attempt to recruit a general adult population of alcohol dependence, with few strict exclusion criteria in keeping with a 'real-world' comparative effectiveness design.

6.1 Inclusion Criteria

1. Adults (age >18 y.o.)
2. Spanish- or English-speaking and able to understand study procedure and provide informed consent
3. Current (within the last year) DSM-V diagnosis of alcohol use disorder as determined by the study physician and standard DSM-V checklist.
4. Endorses goal of alcohol abstinence, and is able to achieve alcohol abstinence without inpatient detoxification, per study physician.

6.2 Exclusion Criteria

1. Current opioid dependence and/or positive urine toxicology for extended opioids.
2. Pregnancy or female and planning conception.
3. Allergy to naltrexone or the PGL XR-NTX formulation or diluent.
4. Severe liver disease, liver failure, or liver function test levels greater than three times normal.
5. Other severe, untreated or uncontrolled medical illness (e.g., severe heart failure or dementia).
6. Untreated psychiatric disorder that might make participation hazardous (e.g. untreated psychosis, bipolar disorder with mania, significant suicide risk).

7.0 Study Procedures

7.1 Recruitment and Pre-screening

Recruitment will consist of both in-clinic referrals of existing primary care patients, as well as community recruitment of patients new to primary care. Recruitment will rely on the successful blend of 'in-reach' (meetings with clinicians, detailing, systematic communication) and local area outreach (ads, external detailing) that we employed during our pilot study to prescreen 116 persons, consent 76, and enroll 72 eligible persons over a 13-month period (a rate of 5.5 persons enrolled per month, similar to that of the current study). Routine screening for alcohol use is not presently standard practice at the study site. However, if routine alcohol screening launches during the course of the study (SBIRT implementation efforts are on-going within the HHC system), eligible persons identified through SBIRT efforts could be referred to the study. Persons interested in study enrollment will call an intake number, or consult with a research coordinator in-person. A brief eligibility pre-screen will determine probable eligibility, after which patients will be scheduled for a baseline screening visit. Recruitment will be patient- or provider-initiated rather than initiated by the research team. Potential subjects will not be approached at random by research staff at Bellevue clinic or in any other setting unless patient-initiated. Most referrals will come from in-clinic referrals by physicians or by local outreach recruitment ads. Potential participants will call the research team phone number advertised or received from referring physician. Research coordinators will complete a pre-screening on the phone with potential subjects to do an initial assessment of eligibility. If potential participants are deemed initially eligible (based on phone-screen) by study staff and the PI, research coordinators will schedule the initial Screening Visit with subject at Bellevue Hospital. All documents containing PHI on pre-screen interviews of potential subjects pre-screened on telephone and found to be ineligible or not interested in study will be destroyed. The only information that will be retained from ineligible pre-screens will be gender and age. Participants will also be recruited through word of mouth referrals. Participants can earn a \$50 referral bonus for each eligible person referred and successfully

randomized into this study. All participants will be provided travel reimbursements in the form of MetroCards at the end of every study visit.

7.2 Screening and Randomization

At the baseline visit, informed consent will be obtained and eligibility confirmed by the research coordinator and study physician. A subsequent randomization/treatment visit will then be scheduled within a 2 week time period. Several factors may be associated with naltrexone treatment success/failure. We will stratify urn randomization by gender and recruitment status (in-clinic vs. community referrals). Stratifying further, however, yields increasingly smaller cells, given 117 per arm; AA ethnicity, medication preference (monthly injectable vs. daily oral), and lead-in (3-day) abstinence will be analyzed as a priori predictors of effectiveness. Randomization is the starting point of the study (day 1, week 1).

7.3 Study Interventions: Medical Management plus XR-NTX vs. O-NTX

Existing primary care physicians, all board-certified in internal medicine, physician assistants, and registered nurses at an adult primary care clinic, Bellevue Hospital, will be recruited to participate in this trial as MM clinicians. As in our previous studies with XR-NTX and buprenorphine in these sites, study participants may see different individual providers over the course of 24 weeks, thus optimizing visit flexibility as well as enhancing generalizability to multi-provider practice settings. The same study clinicians will provide both XR- and O-NTX treatment. The study site relies primarily on physician visits as the core modality for primary care encounters, and it is expected study visits will be primarily with physicians. Study clinicians will provide all XR-NTX injections in clinic (Ambulatory Care, 2nd floor, Rm. #2111) each month for each participant randomized to the XR-NTX arm. O-NTX, which is a daily oral pill formulation of naltrexone, will be self-administered on a daily basis by O-NTX participants.

The content of the Medical Management component will be the same in both arms, and will be based on the initial and follow-up MM visits outlined in the COMBINE MM manual and adapted by the NIAAA Clinician's Guide.²⁰ MM emphasizes: a) education surrounding the alcohol dependence diagnosis, b) a recommendation and emphasis on drinking abstinence, c) support for 12-step involvement (referrals to specialty outpatient treatment will not be part of the MM strategy – patients interested in such will not be prohibited from self-referral, and specialty referrals will be made in cases of relapse/treatment failure), d) self-efficacy counseling surrounding medication adherence, e) education and trouble-shooting of medication side effects, f) feedback on the success of drinking reductions, g) and non-specific support and motivational enhancement to make further changes toward abstinence.

MM clinician's will be trained at start-up and through quarterly calls and booster session in an adaptive approach consistent with the NIAAA COMBINE trial (see NIAAA COMBINE manual) and in consultation with [name]. Strict standardization and certification of MM clinicians, as was done in COMBINE, will not be pursued, as this would diverge from a pragmatic clinical trial attempting to reflect the adoption of, but not absolute fidelity to COMBINE MM.

7.4 Study Care vs. Usual Care: Participants in both arms may schedule additional MM visits as needed to address medication side effects or unanticipated study-related events. Any such additional visits required will be tracked carefully as service utilization. Telephone support with research coordinators and study clinicians will be available at all times during the study and also tracked as utilization. However, clinicians cannot provide or bill for other routine primary care services, such as blood pressure management or cancer screening, during MM visits. This is a conundrum in any NIH-funded, patient-level clinical trial in primary care, which cannot budget for comprehensive care. Patients can initiate or continue access to all primary care services through the same clinician and in the same clinics, it will simply occur as a non-study visit at either clinical site, both of which are public clinics providing access to all patients regardless of insurance status or ability to pay.

7.5 XR-NTX Plus Medical Management

XR-NTX will be delivered at the point of care as a single, 380mg IM injection (4cc) to alternating upper, outer, gluteal (buttock) quadrants. Injections occur every four weeks. Between-injection MM visits will assess and manage adverse events, treatment effects, and support the goal of alcohol abstinence.

7.6 Oral NTX Plus Medical Management

O-NTX will be provided by the facility's pharmacy following each monthly medication dispensing/injection MM visit, and in keeping with standard ambulatory prescribing practices of a recommended 50mg daily dose.⁸⁰ Participants with means or adequate insurance coverage may instead present their written prescription to an outside commercial pharmacy if they prefer.

7.7 Research-only Assessment Visits

As in any large clinical trial of usual care, some participants in both arms will not be present for all scheduled treatment visits. In an attempt to 'de-link' complete cost, utilization, and longitudinal drinking data collection from a naturalistic observation of these same usual care patterns, we will conduct 3 Research-only Assessment visits at week 13, 25 and 48. These visits will not hinge on a participant's treatment retention status, will be heavily incentivized to encourage participation (\$100 for time and travel), and will be conducted preferably in-person but alternatively by telephone if a participant is otherwise unwilling or unable to appear in clinic. These visits will be carefully scheduled apart from MM treatment visits, which are otherwise not incentivized beyond the provision of no-cost care and medication, so as to minimize the influence of extra assessments, attention, and the monetary research participation incentive on a participant's willingness to continue with MM. Participants will be paid \$20 for the initial screening visit after completion of all research assessments and \$20 after completing the randomization visit.

7.8 Rescue Strategies among Treatment Non-Responders

Clearly many outcomes will occur among the 234 planned participants, beyond drinking reductions, and include: remaining in treatment and tolerating either medication but without beneficial changes to baseline alcohol intake levels; dropping out of all treatment but reporting diminished drinking; or wishing to remain in primary care treatment but unable to tolerate either form of naltrexone. Regarding continued heavy alcohol use, MM already informs and encourages interested patients to access AA, and this recommendation would be particularly relevant to those not responding to pharmacotherapy and amenable to an external referral to more intensive treatment. At any point in the trial, patients who appear to be unable to stop drinking due to severe withdrawal symptoms or who are experiencing severely detrimental consequences of heavy drinking (i.e., job loss, homelessness) will be encouraged to seek admission to inpatient detox and specialty treatment through Bellevue Hospital. Detox and intensive outpatient alcohol specialty services are immediately available to all participants through the Bellevue Hospital Chemical Dependency programs, including same-day admissions to our detox unit, regardless of insurance status or ability to pay. All enrolled participants, however, will be encouraged to remain in their assigned treatment protocols and continue follow-up in primary care for the entire 24 week treatment period, independent of medication side effects, on-going drinking, or intermittent detox or other alcohol-related inpatient treatment episodes. There is little risk, in other words, at keeping participants engaged in primary care MM regardless of on-going, frequent heavy drinking, in which case they would qualify as a primary good clinical outcome failure, or the need for further, more intensive specialty treatment, access to which the MM clinician and study staff may be crucial in facilitating. At the conclusion of the 24 week treatment trial, all patients will be offered further primary care follow-up within the same clinics and referrals to specialty alcohol treatment, if indicated, through these universally accessible addiction specialty services at Bellevue Hospital.

8.0 Assessments and Outcome Measures (Table 2)

Table 2. Visit Frequency (weeks)	0	1 ⁺	3	5 ⁺	7	9 ⁺	13 ⁺	17 ⁺	21 ⁺	25	26	48
XR-NTX vs. O-NTX + MM visits	x [#]	x [#]	x	x	x	x	x	x	x	x	x*	
Research-only assessment visits							x [#]			x [#]		x [#]

- *Safety documentation research visit
- # Compensation provided
- + Medication Dispensed

A comprehensive panel of measures is planned including standard measures of drug and alcohol use, medical status, and on-going treatment services utilization. The Timeline Follow Back (TLFB), Alcohol Use Disorders Identification Test (AUDIT), and Obsessive-Compulsive Drinking Scale (OCDS) are all validated measures used to identify alcohol and drug use along with regular urine toxicology and breathalyzer tests. The ASSIST will be used to assess for substance abuse or dependence and PHQ-9 for psychosocial diagnoses. The Seek, Test, Treat and Retain (STTR) assessment will collect various demographic information for each participant. The Economic Form 90, Cost Survey, and World Health Organization Quality of Life Survey (WHOQOL) will be used to assess treatment and criminal history as well as to ascertain economic data for cost-effectiveness outcome measures. The Morisky Medication Adherence Scale (MMAS-8) will be administered to the O-NTX arm only, providing information on adherence to self-administered medications. Fagerström's test for nicotine dependence and recall of cigarettes per day will be used to assess smoking cessation measures. Adaptations of the Stages of Change Questionnaire (SOC) and Responses to Stress Questionnaire (RTS) will look towards patient motivation, self-efficacy, and coping skills. The DSM-V criteria for PTSD, Generalized Anxiety Disorder 7-Item Scale (GAD-7), and Perceived Stress Scale (PSS) will be used to assess PTSD. Throughout the treatment phase, all adverse events (AEs) will be recorded on an AE form at all treatment visits.

Screening Visit (week 0): Informed Consent Form, Consent Quiz, medication preference question, DSM-V diagnostic interview and checklist, demographics, ASSIST, PHQ-9, WHOQOL, Alcohol Use Disorders Identification Test (AUDIT), Obsessive-Compulsive Drinking Scale, Fagerström, SOC, RTS, Questionnaire, DSM-V checklist for PTSD, GAD-7, PSS, history and physical exam, vital signs, liver function (AST, ALT, GGT), urine toxicology, pregnancy test, blood alcohol breathalyzer.

Randomization Visit (week 1): Medical Management initial visit progress note, baseline biomarkers (CDT, Asp40 OPRM1 genotyping), urine toxicology, and Economic Form 90.

Treatment Visits (week 3-25): Timeline Followback (TLFB), recall of cigarettes per day, Morisky Medication Adherence Scale (MMAS-8, O-NTX arm only), Medical Management follow-up visit progress note, Adverse Event form, labs (weeks 13 and 25 only, AST, ALT, GGT, CDT).

Research-only Assessments* (week 13, 25, 48): TLFB, Economic Form 90, AUDIT, OCDS, WHOQOL, Fagerström**, SOC**, RTS**, DSM-V checklist for PTSD**, GAD-7**, and PSS**.

**Only at weeks 13 and 25.

Banked Genetic and Biomarker Testing: At randomization, participants will provide two separate blood draws (3 teaspoons blood for each) for genotyping and biomarker testing. Each of these blood samples will be labeled with the subject ID number and the date of blood draw only. No identifiable or private health information will be included on the labs prior to and when sent out for testing. Blood samples for a single biomarker (CDT) for heavy alcohol use will be drawn at randomization, weeks 13, and 25, and kept frozen at secure NYUMC facility freezer. At the conclusion of enrollment for study, samples will be sent in large batches to the Medical University of South Carolina (MUSC) and [name], a consultant on this protocol, laboratory. Results filed under the study ID only will be communicated and entered into the study database. Whole blood samples for a single nucleotide polymorphism (SNP) at the mu opioid receptor, the A118G OPRM1 SNP, will likewise be frozen, banked, and shipped in batch fashion for analysis at MUSC by

[name]. All samples will be destroyed following analysis and not preserved for future use. Results from either CDT or OPRM1 will be for research purposes only, will not be considered in real-time or used for participant counseling, and will be analyzed at conclusion of the study as secondary biomarkers and genetic baseline predictors of treatment outcomes.

8.1 Primary Outcome: The primary outcome measure of this study is a binary measure of success/failure consisting of a composite good clinical outcome (yes/no) through the final 20 weeks: abstinence or moderate drinking (≤ 2 drinks/day, men; ≤ 1 drink/day, women; ≤ 2 heavy drinking episodes every 4 weeks [heavy drinking is ≥ 5 drinks/occasion, men; ≥ 4 drinks/occasion, women). Abstinence, drinks/day, and heavy drinking days will be assessed by the TLFB calendar⁸¹ administered at each MM and Research-only visit. As the final MM visit (week 25) does not involve medication prescribing or constitute active treatment, the week 26 research-only assessment visit TLFB will be used to capture complete heavy drinking data among participants missing the final week 25 MM visit.

Rationale: Why a binary good clinical outcome of abstinence or moderate drinking only as the primary outcome, vs. % days abstinent or time to first heavy drinking day? As stated earlier and in the original proposal, we are interested in all of these important alcohol treatment outcomes, and which we will track and report. Our strong preference is to anchor the design of this comparative effectiveness trial on a pragmatic good clinical outcome that would have genuine face validity for both patients and treatment providers. This analytic approach is consistent with pragmatic comparative effectiveness trial designs focusing on simple and important behavioral outcomes, such as post-intervention cancer screening, appropriate post-stroke smoking cessation treatment, or self-reported pain control over time.^{46,47,48,49,50}

8.2 Secondary Drinking, Adverse Events, and Measures: drinking measures will be evaluated at each monthly visit (TLFB), along with self-reported O-NTX adherence (MMAS-8) and adverse events. Liver function tests (aspartate transaminase (AST), alanine transaminase (ALT), gamma-glutamyl transferase (GGT) and carbohydrate-deficient transferrin (CDT) will be measured every three months (week 0/1, 13, and 25), with AST, ALT, and GGT results available in real-time to study physicians. CDT, a validated biomarker for heavy drinking,^{82,83,84} is not in use or available at either facility, and will not be reported to participants or study physicians, but rather used as a secondary marker of baseline and in-treatment heavy drinking. CDT represents a 'cutting edge' alcohol biomarker, and one not previously studied in the context of an XR-NTX treatment trial. Analysis and interpretation of CDT results will be coordinated with [name] and his laboratory. Likewise, baseline assessments of drinking severity and psychiatric function (OCDS,⁸⁵ MINI-SCID,⁸⁶ Form 90⁸⁷) and naltrexone mu receptor susceptibility (Asp40 OPRM1 genotyping) will be captured for research purposes only, and not integrated into the clinician's MM strategies.

8.3 Cost Effectiveness Outcomes: Economic data will be derived primarily from the Economic Form 90,⁸⁸ Non-Study Medical Service and HHC electronic medical records assessments, EQ-5D (functional status),⁸⁹ and a cost survey or standardized question querying patient reports of specific non-medical related costs (including lost/gained work, lost/gained dependent care, transportation costs, arrests, motor vehicle accidents) collected at baseline and at week 13, 25, and 48 assessments. The week 48 assessment is included to gain longitudinal, post-treatment cost, drinking, and functional data at a small cost to the overall study budget. Whenever possible, verification of productivity (paystubs) and medical costs (medical records) will be sought to corroborate self-report.

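### Pregnancy is an exclusion, but the only listed test is at week 0; none is listed at the six dispensing visits, which matters most for XR-NTX

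*Combined protocol and SAP*

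**What the plan says.** Section 6.2 lists as an exclusion "Pregnancy or female and planning conception". Section 8.0 then gives the procedures visit by visit:

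- **Week 0 (screening):** the list ends with "urine toxicology, pregnancy test, blood alcohol breathalyzer".
- **Week 1 (randomization, first dose):** a progress note, then "baseline biomarkers (CDT, Asp40 OPRM1 genotyping), urine toxicology, and Economic Form 90". Urine toxicology is repeated; the pregnancy test is not.
- **Weeks 3 to 25 (treatment):** the only laboratory item is "labs (weeks 13 and 25 only, AST, ALT, GGT, CDT".
- **Weeks 13, 25 and 48 (research-only):** interviews and questionnaires, no pregnancy test.

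Table 2 marks medication as dispensed at weeks 1, 5, 9, 13, 17 and 21. On the time from screening to the first dose, section 7.2 says: "A subsequent randomization/treatment visit will then be scheduled within a 2 week time period". For the depot arm, section 7.5 says: "Injections occur every four weeks. Between-injection MM visits will assess and manage adverse events". Section 7.6 describes the oral arm as following "standard ambulatory prescribing practices of a recommended 50mg daily dose". During treatment, section 8.0 provides that "all adverse events (AEs) will be recorded on an AE form at all treatment visits".

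**The concern.** Pregnancy status can change during a 24-week treatment period without anyone noticing at first. The plan treats pregnancy as a reason not to start naltrexone, yet it schedules no further check once treatment begins. Its other laboratory-based exclusions are each rechecked at least once: liver enzymes at weeks 13 and 25, and urine toxicology at week 1.

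The stake is participant safety, not the validity of the trial's comparison. A woman whom the plan would have turned away at entry could receive further doses with no scheduled step to reveal the pregnancy.

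The weight falls on XR-NTX. An injection acts for four weeks and cannot be removed, whereas a daily tablet can be stopped on any day. Section 12.1 draws this contrast itself, although it does so for pain management. Applying it to pregnancy is an inference.

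**Working it through.** The plan gives no figure of its own to reproduce, so the check is a count followed by bounding arithmetic.

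**1. Coverage of dosing by testing.** Dispensing visits (Table 2): {1, 5, 9, 13, 17, 21} = 6. Visits with a listed pregnancy test: {0}. Overlap: 0 of 6. The last dispensing is 21 − 1 = 20 weeks after the first, so up to 20 + 2 = 22 weeks after the only test.

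**2. Blind period before the first dose.** Let L be the weeks from conception until urine turns positive. L is assumed to be 2, with a range of 1 to 3. With a test at week 0 only and a wait of up to 2 weeks, the first dose is blind to conceptions in the preceding L + 2 = 4 weeks (3 to 5). A test at week 1 shortens this to L = 2 weeks (1 to 3). A conception that the week 0 test misses could be followed by up to 6 injections.

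**3. Further injections after a conception during treatment (XR-NTX).**

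| Conception in weeks | Injections still to come |
|---|---|
| 1–5 | 5 |
| 5–9 | 4 |
| 9–13 | 3 |
| 13–17 | 2 |
| 17–21 | 1 |

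With conception spread evenly, the mean is (5 + 4 + 3 + 2 + 1)/5 = 15/5 = 3.0. This assumes full attendance and no detection by other means, so it is an upper bound. Section 9.0 predicts that 40–50% complete XR-NTX. Crediting injections to completers only gives 3.0 × 0.4 = 1.2 to 3.0 × 0.5 = 1.5. That is too low as a correction for attendance, because non-completers also receive some injections.

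**4. Effect of a test before each injection.** Only conceptions in the last L weeks of each four-week interval are missed, and each costs one injection. The mean is L/4 = 2/4 = 0.5 (0.25 for L = 1, 0.75 for L = 3). The reduction is 1 − 0.5/3.0 = 83% (92% to 75%). A test at week 1 alone leaves the 3.0 unchanged, because it cannot detect later conceptions.

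**5. How often this would arise.** The documents do not give the proportion of women, the proportion able to conceive, or a conception rate. Assume 20–40% women, 30–60% of them able to conceive, and 1–5% conceiving in 24 weeks:
- Women able to conceive: 234 × 0.2 × 0.3 = 14.0 to 234 × 0.4 × 0.6 = 56.2.
- Half of these on XR-NTX: 7.0 to 28.1.
- Pregnancies on XR-NTX: 7.0 × 0.01 = 0.07 to 28.1 × 0.05 = 1.4.

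The twenty-fold range shows that the number is not known. It supports only the statement that pregnancies should be rare.

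**The case against.** **The visit lists are not exhaustive.** Section 8.0 promises regular urine toxicology and breathalyzer tests that the week 3 to 25 list omits. Section 8.3 promises the EQ-5D and cost survey, which appear in no list. Absence from a list is therefore weaker evidence than it seems. This stands in part. But for those items other text makes the promise, and no text anywhere promises a repeat pregnancy test.

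**Pregnancy would often be noticed anyway.** Clinicians see participants at weeks 3, 5, 7, 9, 13, 17 and 21 with an adverse event form, and telephone support and extra visits are available (section 7.4). This stands, and it is why 3.0 is a ceiling. It does not help in the early weeks, when a pregnancy may not yet be recognised. After week 9, the next scheduled treatment visit through week 21 is always the next injection.

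**The trial follows usual care.** Section 12.1 declines to exclude on body habitus because that lies outside usual practice, and monthly testing might be resisted on the same ground. But pregnancy is an exclusion that the plan chose, so the question is whether that criterion is maintained.

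**Stronger readings.** A reader might infer that the plan has no rule to stop naltrexone in pregnancy, particularly because section 7.8 encourages everyone to stay on assigned treatment. The documents do not support that conclusion: the consent pages were removed and the Medical Management manual is not supplied, so such instructions may sit there. Section 12.6.4 also makes congenital defects a serious adverse event. That is outcome reporting, not testing, but pregnancy outcomes are not wholly ignored. A reader might also infer that naltrexone should stop whenever a participant says she plans to conceive. An entry exclusion is not automatically a stopping rule, and stopping would have to be weighed against a return to heavy drinking.

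**Conclusion.** The point holds as a narrow matter of the testing schedule. The only listed pregnancy test is at week 0, up to 2 weeks before the first dose, and 0 of 6 dispensing visits list one. It is a cheap improvement in patient safety, and it matters most for XR-NTX.

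The mean of 3.0 further injections should not be read as the expected exposure of a pregnant participant. It applies only if conception occurs, all injections are attended and no one detects the pregnancy. The fall to 0.5 also depends on the assumed two-week lag to a positive urine test. Nor should the point be read as a finding of fetal harm: the documents describe none, and the argument rests only on the plan's own exclusion.

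The power calculation and the primary drinking analysis are unaffected.

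**What to change.** For women able to become pregnant:

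1. Add to the section 8.0 visit lists a urine pregnancy test, read before dosing, at week 1 in both arms. Urine is already collected at that visit for toxicology.
2. Add the same test before each later XR-NTX injection (weeks 5, 9, 13, 17 and 21).
3. State that the next dose is withheld on a confirmed positive, and that the participant stays in MM visits and assessments. This also keeps her follow-up data for the intention-to-treat comparison in section 10.1.

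No new visits are needed. Under the assumed proportions above, the number of tests is 14.0 + 5 × 7.0 = 49 to 56.2 + 5 × 28.1 = 197 (the latter from unrounded values), plus a short amendment. Full attendance is assumed, so fewer would be done in practice. Testing at every oral dispensing as well would take 6 × 14.0 = 84 to 6 × 56.2 = 337 tests, for less gain because tablets can be stopped on any day.

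The main downside is an occasional dose delayed while a false positive is resolved. If the clinic already tests before injections, one sentence in section 8.0 recording this is enough.
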